8.5.3 Safety analyses

The adverse events will be presented descriptively by means of frequency and percentages to evaluate both the rate of incidence and event occurrence among the different treatment groups. The descriptive tables will be presented with respect to intensity, seriousness and relationship to the treatment.

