3 OVERALL STUDY DESIGN/OVERVIEW OF DESIGN

EXCALIBUR is a phase II study.

Excalibur 1 is a three-armed RCT comparing 2nd line systemic chemotherapy to liver transplant and to HAI. Because of the transplant arm, this sub-trial has somewhat stricter inclusion criteria.

Excalibur 2 is a two-armed RCT conducted within the same framework as *Excalibur 1*, but without the transplant arm, and with somewhat wider inclusion criteria (see figure). For analysis, the HAI arm and the systemic chemotherapy arm of *Excalibur 1* and 2 will be directly comparable (stratified for age and primary tumour resected/in situ) and hence boost numbers for this comparison.

[figure not shown]
Study period:

Estimated date of first patient enrolled: February 2021

Anticipated recruitment period: 3 years

Estimated date of last patient completed: November 2024

Treatment duration: up to 2 years

- HAI (intervention group 2) and Systemic therapy (control arm, group 3): Until progression or resection, up to two years
- Transplant (intervention group 1): Until transplant or until removal from list.

Follow-up for outcomes: 10 years

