6.2.3 Duration Period for Reporting AE and SAE

Any new primary cancer (non-related to the cancer under study) should be recorded in the CRF.

For each patient the standard time period for collecting and recording of AE and SAEs in the CRF (reporting of SAE to sponsor) will begin at start of study treatment and will continue for at least 30 days following the last dose of study treatment for each patient in patients receiving FUDR.

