8 STATISTICAL METHODS AND DATA ANALYSIS

8.1 Determination of Sample Size

We estimate an overall survival at two years in the standard care group (group 3) to be 30 %. We aim to decide whether the use of HAI (group 2) can increase this to 75 % and if liver-TX (group 3) can increase this to 90 %. For a two-sided parallel-group test of proportions to answer both questions with a power of 0.80 and an alpha of 0.05, this will require 16 completed patients per group 3 and 2 to show superiority for HAI over standard care (systemic chemotherapy). An additional 7 patients is needed in the transplant group (1) to show superiority over standard care group (3), bringing the total to 39 patients. This is based on a three-year accrual time, and a total of five-year follow-up from the first patient, ensuring at least two years follow-up for all patients. The trial is not powered to show a difference between group 2 and 1. Adding 15 % to allow for drop-outs, we aim to randomise a total of $18 + 18 + 9 = 45$ patients in a 2:2:1 ratio.

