8.5.5 Descriptive statistics

All categorical (including binary and ordinal) data will be summarized using frequency counts and percentages of patient incidence. Percentages will be calculated using the appropriate study population; any exceptions to this will be highlighted in the table footnote. Continuous variables will be summarized using number of patients (N), mean, standard deviation (SD), median, 25/75 percentile and range (minimum/maximum)

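### Section 8.5.3 reads an incidence rate off patient percentages, although time under adverse-event observation differs by arm, so accruing non-fatal events are not comparable between arms

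*Protocol*

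**What the plan says.** Section 8.5.3 sets the safety analysis: "The adverse events will be presented descriptively by means of frequency and percentages to evaluate both the rate of incidence and event occurrence" by treatment group, with tables split by intensity, seriousness and relationship. Section 8.5.5 confirms that categorical data are reported as "frequency counts and percentages of patient incidence". The protocol mentions no person-time denominator, median observation time or common window.

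Several sections determine how long a patient is observed for adverse events:

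- **Section 3.** HAI and control patients are treated until progression or resection, for at most two years. For the third arm the rule is "Transplant (intervention group 1): Until transplant or until removal from list". The synopsis gives treatment duration as 24 weeks.
- **Section 6.2.3.** Collection starts with study treatment and "will continue for at least 30 days following the last dose of study treatment", but this end is stated only for patients receiving FUDR.
- **Sections 5.11 and 6.4.** The first collects events at each visit; the second records them throughout the trial until they resolve.
- **Section 5.6.5 and Table 7.** Resected or transplanted patients have visits for up to 10 years. After progression or toxicity there is an end-of-treatment visit, then survival only.
- **Section 8.1.** "We estimate an overall survival at two years in the standard care group (group 3) to be 30" per cent. The trial asks whether HAI can "increase this to 75 % and if liver-TX (group 3) can increase this to 90" per cent. (The transplant arm is labelled group 3 there and group 1 elsewhere.)
- **Sections 6.1.4 and 6.2.2.** Death is a serious adverse event, including death from progression.

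**The concern.** The protocol names a method and gives it a purpose, comparing how often events occur across arms, that the method serves only when time at risk is similar. A patient who dies at month 6, or whose follow-up drops to survival status after progression, cannot contribute a later non-fatal event. A patient who is resected and seen for years can. The percentage then mixes the event rate with the length of observation.

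Section 10 expects the side effects of the regimens to be roughly in balance despite the added laparotomy. A table that confounds toxicity with observation time is a poor basis for judging that.

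**Working it through.** **1. The plan's own figures.** The protocol gives no figure for adverse-event exposure, so the inputs are the survival rates of section 8.1. These are the ones behind the sample size, a "two-sided parallel-group test of proportions" "with a power of 0.80 and an alpha of 0.05". The unpooled formula n = (1.960 + 0.842)² × [p1(1−p1) + p2(1−p2)] / (p1−p2)² gives:

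- 30% v 75%: 7.849 × 0.3975 / 0.2025 = 15.41, so 16
- 30% v 90%: 7.849 × 0.30 / 0.36 = 6.54, so 7

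The total is 16 + 16 + 7 = 39, and 39 × 1.15 = 44.85, so 45. The stated sample size reproduces.

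**2. Time alive to 24 months.** Assume constant death hazards h = −ln(S)/24. Mean time alive is (1−S)/h.

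| | Control | HAI | Transplant |
|---|---|---|---|
| S at 24 months | 0.30 | 0.75 | 0.90 |
| h per month | 0.0502 | 0.0120 | 0.0044 |
| Mean months alive | 13.95 | 20.86 | 22.78 |
| Ratio to control | 1.00 | 1.49 | 1.63 |

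**3. Percentages at an identical event rate, collection while alive to 24 months.** The share with at least one non-fatal event before death is r/(r+h) × (1 − exp(−(r+h)t)). The documents give no event rate, so r is an assumed range.

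| r per month | Control | HAI | Transplant | HAI excess | Transplant excess |
|---|---|---|---|---|---|
| 0.02 | 23.2% | 33.5% | 36.3% | 10.3 | 13.1 |
| 0.05 | 45.4% | 62.4% | 67.0% | 17.0 | 21.6 |
| 0.10 | 64.8% | 83.2% | 88.0% | 18.4 | 23.2 |

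The true rate ratio is 1.00 in every row. At r = 0.05 the expected events per patient are 0.70, 1.04 and 1.14. Divided by the mean months in step 2, each returns 0.05 per patient-month.

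**4. The same with a 24-week window** (168/30.4375 = 5.52 months). The time ratios fall to 1.11 and 1.13.

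| r per month | Control | HAI | Transplant | HAI excess | Transplant excess |
|---|---|---|---|---|---|
| 0.02 | 9.2% | 10.1% | 10.3% | 1.0 | 1.2 |
| 0.05 | 21.2% | 23.4% | 23.8% | 2.2 | 2.6 |
| 0.10 | 37.5% | 41.2% | 42.0% | 3.6 | 4.4 |

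**5. Collection that follows study treatment.** Time to progression, resection or transplant now drives exposure. As an illustration, assume exponential times to end of treatment with medians of 4 to 6 months (control), 6 to 12 (HAI) and 2 to 4 (transplant waiting time). These medians are not in the documents. At r = 0.05 the shares are 22–30%, 30–43% and 13–22%. The transplant arm moves from the highest percentage to the lowest.

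**6. Rows that include death.** Counting death as an event, the share is 1 − exp(−(r+h)·24). At r = 0.05 this is 91% (control), 77% (HAI) and 73% (transplant), the opposite order to step 3.

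**7. Precision.** For 18 v 18 patients the 95% half-width of a difference is 1.96 × √(2p(1−p)/18): 29.9 points at p = 0.3 and 32.7 at p = 0.5.

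**The case against.** A reader might infer that the planned table must make the longer-surviving arms look about 17 to 22 points more toxic. The documents do not support that.

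- **Window.** Those points come from r = 0.05 with collection for as long as patients live, up to 24 months. The protocol does not settle on that window. Steps 4 and 5 show that the distortion may be small, or reversed for transplant. This stands, and it is why the window has to be reconciled first.
- **Deaths.** Because progression deaths are serious adverse events, any row that includes them favours the arms with fewer deaths (step 6). This stands. The point is confined to non-fatal events.
- **Procedural harms.** Pump-placement and other surgical complications arise per operation, and a patient percentage is the natural measure for them. This stands.
- **Competing-risk methods.** Cumulative incidence with death as a competing event might look like the cure. It is not: the formula in step 3 is that quantity. At equal rates of 0.05 it still gives 35, 42 and 44% at 12 months and 23, 25 and 26% at 6 months. The gap narrows because the horizon is shorter.
- **Noise.** In a descriptive table with about 18, 18 and 9 patients, sampling error exceeds the distortion. This limits the consequence but does not make the percentages a rate.
- **The analysis plan.** Section 8.4 defers detail to a separate plan, not available here, which may add exposure-adjusted rates. That would answer the point in practice. The finding rests on what section 8.5.3 itself fixes: a method and a purpose that do not match.

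**Conclusion.** The concern holds in a limited form. Patient percentages alone cannot support the comparison of incidence that section 8.5.3 wants, for non-fatal adverse events that accrue over time. Observation time differs by arm through survival, stopping events, a window tied to last dose and closed only for FUDR patients, and visits that continue only after resection or transplant.

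The upper scenario is an excess over control of about 10–18 points (HAI) and 13–23 points (transplant) with no true difference. The lower scenario is about 1–4 points, and the sign for transplant is not fixed. These sizes rest on the protocol's survival assumptions, constant hazards, and assumed event rates of 2–10% per month. Since the trial is small and the table descriptive, this is a cheap improvement and does not threaten the primary analysis.

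**What to change.** 1. Reconcile treatment duration (synopsis, section 3) and adverse-event collection (sections 5.11, 6.2.3, 6.4), and state one collection window, with a start and an end, that is the same for all arms.
2. In section 8.5.3 add, by arm, non-fatal grade 3–5 events per patient-month of adverse-event observation, and the median observation time. Show deaths from progression separately.
3. Keep the patient percentages, including for per-procedure surgical complications.
4. Optionally show the cumulative incidence of the first grade 3–5 event, with death as a competing event, at an early common horizon such as 6 months. Label it as description, since it does not correct for unequal survival.

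**Cost.** Mainly programming: section 6.2.4 already records event onset and end dates in the CRF. Treatment timing and death dates are listed in section 7.2 as medical-record content, so their capture in the CRF should be confirmed. If the common window extends past progression, where Table 7 now collects only survival, extra data from local hospitals would be needed. Person-time rates also assume a roughly constant event rate, which suits early or procedural events poorly; that is a further reason to keep the percentages.

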8.5.4 Other analyses (eg health economics, patient reported outcomes etc)

Patient reported outcomes are recorded by the use of EORTC-C30 and the EQ5D questionnaires.

8.5.5 Descriptive statistics

All categorical (including binary and ordinal) data will be summarized using frequency counts and percentages of patient incidence. Percentages will be calculated using the appropriate study population; any exceptions to this will be highlighted in the table footnote. Continuous variables will be summarized using number of patients (N), mean, standard deviation (SD), median, 25/75 percentile and range (minimum/maximum)

9 STUDY MANAGEMENT

9.1 Investigator Delegation Procedure

The principal investigator is responsible for making and updating a “delegation of tasks” listing all the involved co-workers and their role in the project. He will ensure that appropriate training

relevant to the study is given to all of these staff, and that any new information of relevance to the performance of this study is forwarded to the staff involved.

9.2 Protocol Adherence

Investigators ascertain they will apply due diligence to avoid protocol deviations. All significant protocol deviations will be recorded and reported in the Clinical Study Report (CSR).

9.3 Study Amendments

If it is necessary for the study protocol to be amended, the amendment and/or a new version of the study protocol (Amended Protocol) must be notified to and approved by the Competent Authority and the Ethics Committee according to EU and national regulations.

9.4 Audit and Inspections

Authorized representatives of a Competent Authority and Ethics Committee may visit the centre to perform inspections, including source data verification. Likewise the representatives from sponsor may visit the center to perform an audit. The purpose of an audit or inspection is to systematically and independently examine all study-related activities and documents to determine whether these activities were conducted, and data were recorded, analyzed, and accurately reported according to the protocol, Good Clinical Practice (ICH GCP), and any applicable regulatory requirements. The principal investigator will ensure that the inspectors and auditors will be provided with access to source data/documents.

10 RISK VERSUS BENEFIT ASSESSMENT

It is the firm view of the investigators that the potential side-effects of the two interventions in question are more than outweighed by their potential benefit and by the reduced side effects from a sparing effect on standard systemic chemotherapy.

This is a randomized trial where the control arm receives standard systemic chemotherapy. The overall prognosis for this selected group of patients is very poor and 2nd line chemotherapy comes with a range of side effects that are (to a variable extent) tolerated as (today) no other treatment alternative exist. Irinotecan and Oxaliplatin may induce liver toxicity to an extent completely precluding liver surgery.

From the available literature, patients receiving additional intra-arterial chemotherapy (HAI) may expect a better response and greater possibility of reaching surgery (liver resection) and improved overall survival. Patients receiving liver transplant can expect a significantly improved survival compared to standard chemotherapy alone. The hypothesis is that the experimental treatments are better than today's standard treatment and thus more patients will reach resectional surgery in the trial and henceforth in non-trial settings in the future.

The insertion of HAI pump is an operative intervention with marginal operational risk. Apart from a 1-2 % risk of wound dehiscence, there are no significant risks from the surgery as such. General anaesthesia risk is considered negligible. HAI (FUdR) may cause biliary toxicity. These findings have previously been published and are well known as the drugs have been in clinical use for more than 10-years in the US. The well-documented risk of bile duct inflammation resulting from HAI has been significantly reduced with the use of steroids and dose reduction in the event of increasing LFTs. As HAI is assumed to reduce the dosage and cycles necessary of systemic chemotherapy, we believe that the side effects/complications of the two regimens may well be balanced even with a laparotomy only in the intervention groups.

Liver transplant is an established treatment today. It is a major surgical intervention with accompanying risk: those pertaining to major surgery in general and those resulting from prolonged systemic immunosuppression following reception of an allograft. It is nevertheless associated with vastly increased survival for eligible patients with cirrhosis, HCC and even colorectal liver metastases. Again, a successful liver transplant will largely obviate the need for systemic chemotherapy.

For society, such a study with a positive outcome (experimental treatment better than current treatment) would be of immediate value. A positive study result will mean that patients in the future can be offered better treatment than today's standard treatment – a standard treatment with very poor outcome.

A positive study will form the basis for more use of the experimental treatments; while a negative study will clarify that there is no intention of offering future patients such treatment. For the community it is also important to clarify whether or not the experimental treatment options are effective. A treatment that is not effective should not be offered to future patients.

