8.5 Statistical Analysis

8.5.1 Primary analysis

- Primary variable: Overall survival at 2 years from randomization
- Assessment: From the electronic medical records (EPJ)
- Metric: Hazard ratio
- When the last recruited patient has reached two years follow-up or censor.

The primary analysis will be done by Cox regression with treatment group as covariate, adjusted for stratification factors in the randomization.

Primary population: By intention-to-treat (ITT), i.e. all randomized patients regardless of protocol adherence.

The treatment effect will be presented as hazard ratios between the two treatment groups and the standard of care group, in addition to 95% confidence intervals.

The null hypothesis to be tested is that there is no difference between the treatment groups on overall survival after 2 year. If the null hypothesis is rejected on a 5% significance level, the pairwise treatment group's differences will be tested on the 5% level with the family-wise error rate sustained by the closed test principle.

There will be no handling of missing values. All patients will be followed-up until 2 years or death of any reason. Patients lost to follow-up will be censored at time of last observation, and handled accordingly.

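### Section 10 says a negative study will settle that HAI and transplantation are not to be offered, but a non-significant result from 18, 18 and 9 patients cannot show that either is ineffective

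*Protocol*

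**What the plan says.** Section 10 (Risk versus benefit assessment) closes by attaching a consequence to each result. A positive study, meaning that the experimental treatment is better than the current one, is to be the basis for wider use, "while a negative study will clarify that there is no intention of offering future patients such treatment". Two sentences later it adds: "A treatment that is not effective should not be offered to future patients".

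The protocol gives no separate definition of a negative study. The nearest thing to one is the testing rule in section 8.5.1: a global test of no difference in survival, then "If the null hypothesis is rejected on a 5% significance level, the pairwise treatment group's differences will be tested on the 5% level", under the closed test principle. The same section asks for hazard ratios of each experimental group against standard care with 95% confidence intervals. It attaches no rule to those intervals for concluding lack of effect.

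Section 8.1 gives the effects the trial was sized for. Control: "We estimate an overall survival at two years in the standard care group (group 3) to be 30"%. HAI: "We aim to decide whether the use of HAI (group 2) can increase this to 75"%. Transplantation: "can increase this to 90"%. The calculation is "For a two-sided parallel-group test of proportions to answer both questions", "with a power of 0.80 and an alpha of 0.05". It leads to 18 control, 18 HAI and 9 transplant patients.

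**The concern.** Read together, the section 10 sentences treat a negative study as evidence that the treatments do not work. A superiority test does not provide that. Failure to reject says that the data are compatible with no difference. Whether they are also compatible with a useful difference depends on the width of the interval, and with 18, 18 and 9 patients the interval is wide.

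The trial was sized for gains of 45 and 60 percentage points. A smaller gain that many would still value could easily give a non-significant result. If the sentence were followed, that result would be reported as a reason not to offer the treatment, although no evidence against the smaller gain had been obtained. The sentence also speaks of one study outcome, whereas 8.5.1 has two comparisons against control with very different precision.

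**Working it through.** **Inputs.** From 8.1: two-year survival 30% (control), 75% (HAI), 90% (transplant); two-sided 5%; power 80%; 16, 16 and 7 completed patients; 18, 18 and 9 randomised. From 8.5.1: Cox regression by intention to treat, follow-up until two years or death, global test then pairwise tests at 5%. Assumption made here: a true two-year survival of 60% in an experimental arm (2 × 30%), with exponential survival where a time-to-event method is used.

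**1. The plan's own figure.** With the unpooled two-proportion formula, n = (1.960 + 0.842)² × (0.30 × 0.70 + 0.75 × 0.25) / 0.45² = 15.4, so 16 per group, as stated. For 30% against 90%, 16 against 7 patients gives power 0.83, consistent with 7. Then 16 + 16 + 7 = 39, and 39 × 1.15 = 44.85, so 45. At 18 against 18, power for the 75% target is 0.80 (pooled normal) to 0.84 (Schoenfeld). The sample-size arithmetic is not in question.

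**2. Miss rates for a true 60%.** The hazard ratio is ln 0.6 / ln 0.3 = 0.424. Expected two-year deaths are 18 × 0.7 + 18 × 0.4 = 19.8 for HAI against control, and 18 × 0.7 + 9 × 0.4 = 16.2 for transplant against control. Schoenfeld power is Φ(|ln 0.424| × √(deaths × allocation product) − 1.96):

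- HAI: Φ(0.857 × √(19.8 × 0.25) − 1.96) = 0.48.
- Transplant: Φ(0.857 × √(16.2 × 2/9) − 1.96) = 0.37.

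The miss rate is one minus power:

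| Method, two-year data | HAI, 18 v 18 | Transplant, 9 v 18 |
|---|---|---|
| Pooled normal | 1 − 0.437 = 56% | 1 − 0.319 = 68% |
| Exact enumeration, uncorrected chi-square | 1 − 0.493 = 51% | 1 − 0.321 = 68% |
| Exact enumeration, Fisher | 1 − 0.356 = 64% | 1 − 0.284 = 72% |
| Exact enumeration, continuity-corrected | 1 − 0.356 = 64% | 1 − 0.205 = 79.5% |
| Schoenfeld | 1 − 0.479 = 52% | 1 − 0.369 = 63% |
| Simulated Cox, pairwise only | 53% to 57% | 67% |
| Simulated Cox, global test first | 54% to 64% | 72% |

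The range for HAI in the last row depends on the true transplant effect (90%, 60% or 30%). The transplant entry in that row takes HAI at 60% too.

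**3. If Cox regression used all follow-up.** With three-year accrual and analysis when the last patient reaches two years, the HAI miss rate falls to about 41% to 46% pairwise. With the global test first it is about 43% to 53%, again depending on the transplant effect. For transplantation it is about 59% pairwise (1 − 0.414) and 65% with the global test (1 − 0.354).

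**4. Other assumed alternatives (chi-square / Fisher).** HAI: 74% / 84% missed at a true 50%, and 26% / 39% at 70%. Transplant: 82% / 86% at 50%, and 49% / 52% at 70%.

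**5. What a non-significant result would look like.** Take 5/18 alive on control and 10/18 on HAI. The difference is 0.278, with standard error √(0.278 × 0.722/18 + 0.556 × 0.444/18) = 0.158. The 95% interval is 0.278 ± 0.309, about −3 to +59 points, with chi-square p about 0.09. The observed rate doubles and the interval contains the 45-point target of 8.1, yet the test does not reject.

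**6. How often the interval could support a negative conclusion.** Take a 20-point gain as an assumed worthwhile benefit. If HAI truly has no effect, only 26% of non-significant 18 v 18 trials have a 95% Wald interval that excludes it. If HAI truly gives 60%, under 1% exclude 20 points, and 31% exclude even the 45-point target.

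**The case against.** Several points on the other side stand.

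- **Status of the sentence.** It belongs to the risk-benefit rationale. Section 8 does not refer to it, and no analysis or stopping rule depends on it. A reader might infer that section 10 fixes a binding decision rule; the text does not go that far.
- **Meaning of negative.** That it means p above 0.05 is an inference. It is the only reading for which the protocol offers a rule, but it is not a stated definition.
- **Intervals are already required.** 8.5.1 asks for 95% confidence intervals, so a published result would show its own uncertainty.
- **Baseline.** A reader might infer that the trial could take away a treatment now in use. Section 1.7 says that HAI is not offered in Norway and that these patients are not acceptable for the liver transplant protocols. Section 4.1 says that transplantation is not standard for colorectal cancer. Not adopting an unproven treatment after a failed superiority trial is a defensible default and needs no proof of no effect.
- **Benchmark.** The 50%, 60% and 20-point figures are assumptions. Any small phase II trial has low power below its design effect.
- **Fragility for HAI.** A miss rate of at least half is borderline: the most favourable two-year test gives 50.7%, and longer follow-up can take it below half.

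These points limit the weight of the concern but do not remove it. Declining to adopt a treatment for want of proof differs from stating that the study will have clarified the matter, with ineffectiveness as the reason. Section 10 says the latter.

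**Conclusion.** The point holds as a fault of interpretation in section 10. The sample size and the planned test are not at fault. With 18, 18 and 9 patients and targets of 75% and 90%, a non-significant comparison cannot establish that a treatment is ineffective. For a true rise from 30% to 60%, two-year data would miss the effect in about 51% to 64% of trials for HAI and about 63% to 80% for transplantation. With follow-up beyond two years the HAI figure is about 41% to 53%. 8.5.1 describes follow-up until two years or death, which favours the higher range, but 8.1 also mentions five years from the first patient. For transplantation, more than half are missed under every method tried.

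The figures rest on the protocol's 30% control rate, on 60% as an illustrative alternative, and on exponential survival in the time-to-event calculations. A reader might also conclude that 8.5.1 must contain a numerical futility margin. The documents do not require that: this is a superiority trial, and such a margin is optional.

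**What to change.** Reword the section 10 sentence to say three things:

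1. A non-significant comparison with standard care does not establish that the treatment is ineffective.
2. HAI and transplantation are interpreted separately, each from the 95% confidence interval already required in 8.5.1.
3. A comparison is reported as inconclusive where that interval still includes a worthwhile benefit, including the protocol's own targets in 8.1.

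The intervals in 8.5.1 are for hazard ratios. Under proportional hazards the 8.1 targets correspond to ln 0.75 / ln 0.30 = 0.24 for HAI and ln 0.90 / ln 0.30 = 0.09 for transplantation, so they can be compared directly. If the sponsor wishes to name a smaller minimum benefit, its size is for the sponsor to choose and justify.

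The cost is a change of wording. No analysis, data item or patient number changes. The sponsor gives up the claim that the trial can give a definitive negative answer.
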